# 5.4. Procedures for Monitoring Subject Compliance

Given that a single injection of the study drug will be provided by the investigational center personnel in the clinic, monitoring of subject compliance will not be necessary.

# 5.5. Total Blood Volume

The total volume of blood to be collected for each subject in this study is approximately 909 mL, as provided in Table 2.

Type of samples	Volume per sample (mL)	Total number of samples	Total volume (mL)
Pharmacodynamics (serum P and E2) -before study drug injection -if ovulation by week 52 -if no ovulation by week 52	about 10 (for both P and E2)	up to 7 up to 48 up to 58	~70 ~480 ~580
Pharmacokinetics (serum MPA) -before study drug injection -if ovulation by week 52 -if no ovulation by week 52	about 5	1 up to 48 up to 50	5 ~240 ~250
Hemoglobin	about 4	1	~4
Liver Function	about 5	4	~20
Total a		~121	~924

Table 2:Approximate Blood Volumes

a These are maximum figures, assuming a subject does not ovulate before week 78. The sampling schedule for Part 2 may be reduced further based on assessment of Part 1 data.

~=approximately, P=progesterone, E2=estradiol.

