# **3.3.** Pharmacokinetic Measures and Time Points

The primary pharmacokinetics measure is serum MPA concentration. For Part 1, blood samples for measurement of serum concentrations will be obtained on days 0 (baseline), 1, 2, 3, 5, 7, 10, 12, 14, 18, 21, 28, 35, and 42; weeks 8, 10, 12, 13, 15, 17, 19, 21, 23, 25, 26, 28, 30, and 32; and then every 28 days until week 52, regardless of ovulation status.

Among subjects in whom ovulation has not returned by month 12 (week 52), blood samples for MPA will be tested up to 2 more times (once at week 61 and once at week 74), but not past return to ovulation. The sampling schedule and duration of MPA testing may be modified based on accumulating data for a more accurate characterization of the pharmacokinetic profile of TV-46046. In addition, blood samples will also be collected and stored for possible future MPA testing (if necessary) at all weekly visits when samples are collected for serum progesterone and estradiol, except for pre-treatment visits and visits for confirmation of ovulation.

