# 3.4. Pharmacodynamic Measures and Time Points

The primary pharmacodynamics measure is serum progesterone concentration. Blood samples for measurement of progesterone and estradiol will be obtained as follows: on day 0 (baseline); then at day 7 and then weekly through week 32, regardless of ovulation status. If ovulation does not return by week 32, then weekly blood samples for serum progesterone and estradiol will continue to be collected until ovulation or through week 52, whichever is earlier. If there is no ovulation by week 52, then blood samples for serum progesterone and estradiol will be collected weekly between weeks 61 through 65 and between weeks 74 through 78, but not past return to ovulation.

At any time point during follow-up, a subject with progesterone  $\geq$ 3.0 ng/mL will be asked to return within 5 days for repeated progesterone measurement to ensure close monitoring of the potential post-ovulatory rise of progesterone. If the repeated measurement within 5 days is at or below 3.0 ng/mL, the subject will continue follow-up per her visit schedule. At any time point during follow-up, a subject with initial progesterone  $\geq$ 4.7 ng/mL will be asked to return within 5 days for repeated progesterone measurement for more accurate ascertainment of ovarian function.

Estradiol will be measured at the same time points as progesterone as a supporting pharmacodynamics measure.

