- a For subjects in whom ovulation returns before month 12 post-injection, the final study visit will be scheduled at month 12. If ovulation occurs between months 12 and 18 (between weeks 52 and 78), at the time when the defining serum progesterone result becomes available, the study staff will inform the subject that she needs to return within 5 days to the investigational center for the final study visit. For subjects in whom ovulation does not return by month 18, the laboratory visit at week 78 will be considered the final study visit
- b A urine pregnancy test will be performed at enrollment; and during the study, if indicated.
- c Day 0; within the 1st 5 days of the start of subject's menstrual cycle.
- d Blood samples for serum progesterone and estradiol will be collected approximately twice weekly during the approximately 2 to 3 weeks preceding the subject's expected menses for confirmation of ovulation (ideally at least 4 measurements).
- e Blood samples for serum progesterone and estradiol will be collected on day 0 (baseline); then at day 7 and then weekly through week 32, regardless of ovulation status. If ovulation does not return by week 32, then weekly blood samples for serum progesterone and estradiol will continue to be collected until ovulation or through week 52, whichever is earlier. If there is no ovulation by week 52, then blood samples for progesterone and estradiol will be collected at weeks 61, 62, 63, 64, and 65; and at weeks 74, 75, 76, 77, and 78, if ovulation has not returned by week 65. During these additional laboratory visits, blood samples will be collected and tested for serum progesterone and estradiol at all visits, but not past return to ovulation.
- f At any time during follow-up, subjects with initial serum progesterone ≥3.0 ng/mL will be asked to return within 5 days for repeated progesterone and estradiol measurement. If repeated progesterone is at 3 ng/mL or below, the subject will continue follow-up per their visit schedule.
- g At any time during follow-up, if the serum progesterone level is ≥4.7 ng/mL, subjects will be asked to return within 5 days for repeated progesterone and estradiol measurement.

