- h Blood samples for MPA will be collected on day 0; then on days 1, 2, 3, 5, 7, 10, 12, 14, 18, 21, 28, 35, and 42; then at weeks 8, 10, 12, 13, 15, 17, 19, 21, 23, 25, 26, 28, 30, and 32; and then every 28 days until week 52, regardless of ovulation status. Among subjects in whom ovulation does not return by week 52, blood samples for MPA will be collected up to 2 more times (at weeks 61 and 74), but not past return to ovulation. Blood samples will also be collected and stored for possible future MPA testing (if necessary) any time samples are collected for serum progesterone and estradiol, except for pre-treatment visits and visits for confirmation of ovulation.
- i Injection site reactions will be recorded on day 0 immediately after the injection (within 10 minutes) and within the 1st hour after injection; at days 1, 2, 3, 5, and 7; week 13 and week 32 visits; at the final visit; and at other visits, if indicated.
- j During laboratory visits, information on adverse events and concomitant medications will not be solicited, but will be documented if reported by the subject.
- k Liver function testing and mood evaluation will be evaluated at the week 13 and week 32 follow-up visits.
-  Menstrual bleeding patterns will be obtained by an interview questionnaire approximately monthly; at scheduled follow up visits (weeks 13 and 32 only); and the final study visit. In addition, in Part 2 menstrual data will be collected weekly via an on-line diary.
- m Part 1 only, prior to enrollment.

Lab=laboratory, MPA=medroxyprogesterone acetate.

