### 3.14.3.2.2. Laboratory Visits

During the laboratory visits, blood samples will be obtained for serum MPA, serum progesterone, and estradiol per the sampling schedule (see Sections 3.3 and 3.4, and Table 1). In addition, the injection site will be observed for ISRs on days 1, 2, 3, and 5; and thereafter, if indicated. Information on adverse events and concomitant medications will not be solicited but documented if reported by the subject.

The following procedures/assessments will be performed during laboratory visits:

- obtain blood sample (up to approximately 15 mL) for serum MPA, serum progesterone, and estradiol per the sampling schedule
- evaluate site of injection for ISRs (on days 1, 2, 3, and 5; and thereafter, if indicated)
- interview about menstrual bleeding pattern once monthly (Part 1 only)
- document adverse event (if reported)
- document concomitant medication (if reported)

Blood samples for MPA will be collected and stored for possible future MPA testing (if necessary) any time when samples are collected for serum progesterone and estradiol, except for pre-treatment visits and visits for confirmation of ovulation.

### 3.14.3.2.3. Laboratory Visits after Week 52

Additional laboratory visits will be scheduled at weeks 61, 62, 63, 64, and 65 for all subjects in whom ovulation did not return by week 52; and at weeks 74, 75, 76, 77, and 78 if ovulation has not returned by week 65. During these additional laboratory visits, blood samples will be collected and tested for serum progesterone and estradiol (all visits) and serum MPA (weeks 61 and 74), but not past ovulation. Blood samples for MPA will be collected at all weekly visits after Week 52 and stored for possible future MPA testing (if necessary).

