# 6.1.3. Blood Sampling and Handling

Blood samples (~5 mL) for pharmacokinetic analysis will be obtained from all subjects via venipuncture at the time points detailed in Table 1.

The date and time of study drug administration and the date and time of each pharmacokinetic sample will be recorded on the source documentation and transcribed onto the CRF.

Blood specimen will be collected into one Vacutainer tube containing no anticoagulant and allowed to set at room temperature for at least 20 minutes, but no more than 40 minutes, to permit clot formation. Samples will be centrifuged at room temperature at 2500 to 3000 revolutions per minute (rpm) (approximately 650 to  $1450 \times g$ ) for 10 to 15 minutes to achieve a clear serum layer over the clotted red cells. Approximately equal portions of the sample will then be immediately transferred into 2 properly labeled polypropylene sample storage tubes. The prepared serum samples will be immediately frozen at -20°C and stored in an upright position until shipment.

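### Section 5.5 says 909 mL of blood and Table 2 says 924 mL, but the current sampling schedule gives about 1,064 mL (Part 2) or 1,044 mL (Part 1)

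*Protocol*

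**What the plan says.** Section 5.5 of the protocol gives a per-subject total and refers to the table for it: "The total volume of blood to be collected for each subject in this study is approximately 909 mL, as provided in Table 2". Table 2 prints a total of about 924 mL in about 121 samples. Footnote a says of the figures: "These are maximum figures, assuming a subject does not ovulate before week 78".

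The table allows up to 58 post-injection progesterone/estradiol (P/E2) draws of about 10 mL and up to 50 post-injection MPA draws of about 5 mL for a subject with no ovulation by week 52. If ovulation occurs by week 52, it allows up to 48 of each.

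The sampling schedule is set elsewhere:

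- P/E2, Table 1 footnote e: "Blood samples for serum progesterone and estradiol will be collected on day 0 (baseline); then at day 7 and then weekly through week 32". Sampling then continues weekly to week 52 if ovulation has not returned. After week 52, Section 3.4 has samples "collected weekly between weeks 61 through 65 and between weeks 74 through 78, but not past return to ovulation".
- MPA, Table 1 footnote h: in addition to the listed MPA days, "Blood samples will also be collected and stored for possible future MPA testing (if necessary) any time samples are collected for serum progesterone and estradiol". Pre-treatment and confirmation visits are excepted.
- MPA after week 52, Section 3.14.3.2.3: "Blood samples for MPA will be collected at all weekly visits after Week 52 and stored for possible future MPA testing (if necessary". On testing, Section 3.3 says "blood samples for MPA will be tested up to 2 more times (once at week 61 and once at week 74".
- Volume, Section 6.1.3: "Blood samples (~5 mL) for pharmacokinetic analysis will be obtained from all subjects via venipuncture at the time points detailed in Table 1".

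**The concern.** There are two faults. The text and the table it cites give different totals, and neither equals the sum of the table's rows. More important, the table's draw counts do not follow from the schedule now in force, although footnote a presents them as maxima.

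At stake is the accuracy of the maximum blood volume that the protocol states for healthy volunteers. The documents set no volume limit, so none is shown to be exceeded. No endpoint, analysis set or test depends on the figure.

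**Working it through.** **Step 1. Reproduce Table 2 (maximum-case rows).**

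- Samples: 7 + 58 + 1 + 50 + 1 + 4 = 121, exactly as printed.
- Volume: 7×10 + 58×10 + 1×5 + 50×5 + 1×4 + 4×5 = 70 + 580 + 5 + 250 + 4 + 20 = 929 mL, against about 924 printed.
- Without the 20 mL of liver tests: 929 − 20 = 909 mL, the figure in the text.

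The change log in Section 16.2 shows the likely origin. Amendment 03 added four liver samples of about 5 mL (20 mL) but raised the total from 909 to 924, which is 15 mL. The sentence above the table stayed at 909.

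**Step 2. Count P/E2 draws after injection, no ovulation by week 78** (Section 3.4, Table 1 footnote e).

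- Weeks 1 to 52, weekly: 52
- Weeks 61 to 65: 5
- Weeks 74 to 78: 5
- Total 62, against 58 in the table; 52 by week 52, against 48.

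SAP Section 11.2 gives the last block as weeks 75 to 78. That would make 61, still above 58.

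**Step 3. Count MPA draws after injection** (Sections 3.3, 3.14.3.2.2 and 3.14.3.2.3, Table 1 footnote h).

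- Scheduled for testing by week 52: 13 (days 1 to 42) + 14 (weeks 8 to 32) + 5 (weeks 36, 40, 44, 48, 52) = 32. Weeks 61 and 74 make 34.
- Collected by week 52, tested or stored: the 52 P/E2 visits plus the seven MPA-only days (1, 2, 3, 5, 10, 12, 18) = 59, against 48 in the table.
- Collected by week 78: 59 + 10 = 69, against 50. For this subject the week 78 visit is the final visit, so the final-visit MPA sample adds nothing.
- Store-only samples: 69 − 34 = 35.

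**Step 4. Totals at 5 mL per MPA sample.**

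- Part 2: 70 + 620 + 5 + 345 + 4 + 20 = 1,064 mL in 7 + 62 + 1 + 69 + 1 + 4 = 144 samples. Against 924: +140 mL, 15.2%.
- Part 1 (no liver tests): 1,064 − 20 = 1,044 mL in 140 samples. Against 909: +135 mL, 14.9%. Against 924: +120 mL, 13.0%.
- Part 2 excess over the row sum of 929 mL: P/E2 4×10 = 40 mL, MPA 19×5 = 95 mL, together 135 mL.

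**Step 5. Sensitivity.**

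| Assumption | Part 2 (mL) | Part 1 (mL) |
|---|---|---|
| P/E2 count corrected only, 50 MPA draws kept | 969 | 949 |
| After week 52, MPA only at weeks 61, 74 and 78 (62 MPA draws) | 1,029 | 1,009 |
| Full schedule, store-only samples of v mL | 889 + 35v | 869 + 35v |

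For v = 1, 2, 3, 4, 5 the Part 2 total is 924, 959, 994, 1,029, 1,064 mL.

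**Step 6. Ovulation at week 52, Part 2.** Table rows: 70 + 480 + 5 + 240 + 4 + 20 = 819 mL. Current schedule: 70 + 520 + 5 + 295 + 4 + 20 = 914 mL, before the repeat P/E2 draw that a progesterone of 4.7 ng/mL or more triggers (about 10 mL, making 924 mL).

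**The case against.** The strongest objection concerns the stored MPA samples, which make up most of the excess. The protocol names no volume for samples that are only stored, and 1,064 mL is the top of the 1 to 5 mL range. If only the 34 tested samples counted, Part 2 would come to 889 mL, below both printed totals. The range should therefore be shown. Five mL is still the best-supported value: Section 6.1.3 gives it for pharmacokinetic samples, and Section 3.14.3.2.2 allows up to about 15 mL per laboratory visit, which is 10 plus 5. Table 2 itself charges 5 mL to 48 MPA samples by week 52 when only 32 are scheduled for testing. Section 5.5 also concerns blood to be collected, not blood tested.

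The synopsis, Section 6.1 and footnote h say MPA is collected, or collected and tested, up to two more times after week 52. Read with Sections 3.3 and 3.14.3.2.3, this is loose wording, not a second schedule. Even the restricted reading gives 1,029 and 1,009 mL.

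The comparator for Part 1 can be disputed. The text does not assign 909 mL to Part 1, and only Table 2 carries the maximum label. Against 924 the Part 1 excess is 13.0%.

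The figures are marked approximate, and 909, 924 and 929 differ by only about 2%. That tolerance may cover the mismatch of totals. It does not cover 4 missing P/E2 draws and 19 missing MPA draws.

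**Conclusion.** The concern holds and is minor. The text, the table total and the row sum disagree (909, 924 and 929 mL), and the stated maximum is too low for the current schedule. On the full schedule at 5 mL per MPA sample, it is 1,064 mL in Part 2 and 1,044 mL in Part 1, about 15% above 924 and 909 respectively.

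The part that needs no assumption about stored samples is the P/E2 count. It alone raises the totals to 969 mL (4.9% above 924) and 949 mL (4.4% above 909). The rest depends on counting stored MPA samples at about 5 mL each.

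The SAP records that Part 2 was never implemented, so 1,044 mL is the figure that matters in practice. The maximum applies only to a subject who has not ovulated by week 78. Over about 82 weeks, 1,064 mL is about 13 mL per week. It is not an upper bound, because repeat progesterone visits (triggered at 3.0 ng/mL or above) add about 10 mL each.

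**What to change.** - Recount Table 2 from Table 1 footnotes e and h: up to 52 P/E2 and 59 MPA draws after injection if ovulation occurs by week 52, and up to 62 and 69 if it does not.
- Give separate maxima for Part 1 and Part 2, and use the same figures in the Section 5.5 text.
- State the volume of a store-only MPA sample, so that the total can be checked.
- Add a note that repeat P/E2 draws are additional. At least one is expected in the row for ovulation by week 52.
- Align the wording on two further MPA samples in the synopsis, Section 6.1 and footnote h with Sections 3.3 and 3.14.3.2.3: collected at every weekly visit after week 52, tested at weeks 61 and 74, and not past return to ovulation.

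The cost is wording and table figures only. No sampling changes. The one drawback is a less favourable stated volume.

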# 6. ASSESSMENT OF PHARMACOKINETICS AND PHARMACODYNAMICS

## 6.1. Pharmacokinetics

Pharmacokinetics of MPA will be evaluated based on individual and mean serum MPA concentration-time profiles and estimated noncompartmental pharmacokinetic parameters (see Section 8.5). All subjects will be assessed for nonzero MPA levels at baseline. The MPA results will not be known until later in the study and, therefore, will not be used as exclusion criteria. Subjects with nonzero MPA levels at baseline (ie, more than 5% of their individual  $C_{max}$ ) will be excluded from the primary pharmacokinetic analyses (see Section 8.5.3). During the study MPA concentrations will be measured at pre-defined time points (see Table 1). In addition, subjects for whom ovulation has not returned by month 12 (week 52), blood samples for MPA will be collected and tested up to 2 more times (at week 61 and week 74), but not past return to ovulation. Based on accumulating data, additional sampling and testing for MPA in one or more study groups in Part 1 and/or Part 2 may be conducted for a more accurate characterization of the pharmacokinetic profile of TV-46046.

### 6.1.1. Part 1: Exploratory Pharmacokinetic Variables

The following non-exhaustive list of non-compartmental pharmacokinetic parameters will be calculated for MPA for each treatment group:

- Cmax
- tmax
- C182 (week 26)
- AUC0-182
- AUC0-∞
- apparent terminal half-life

### 6.1.2. Part 2: Dose-range Finding Variables

The following pharmacokinetic parameters will be calculated for MPA for each treatment and population:

- Cmax
- tmax
- C182 (week 26)
- C210 (week 30)
- AUC0-182
- AUC0-210

- AUC0-∞
- apparent terminal half-life

# 6.1.3. Blood Sampling and Handling

Blood samples (~5 mL) for pharmacokinetic analysis will be obtained from all subjects via venipuncture at the time points detailed in Table 1.

The date and time of study drug administration and the date and time of each pharmacokinetic sample will be recorded on the source documentation and transcribed onto the CRF.

Blood specimen will be collected into one Vacutainer tube containing no anticoagulant and allowed to set at room temperature for at least 20 minutes, but no more than 40 minutes, to permit clot formation. Samples will be centrifuged at room temperature at 2500 to 3000 revolutions per minute (rpm) (approximately 650 to  $1450 \times g$ ) for 10 to 15 minutes to achieve a clear serum layer over the clotted red cells. Approximately equal portions of the sample will then be immediately transferred into 2 properly labeled polypropylene sample storage tubes. The prepared serum samples will be immediately frozen at -20°C and stored in an upright position until shipment.

# 6.1.4. Shipment and Analysis of Samples

One aliquot will remain frozen on site, and another will be sent on dry ice in batches with other samples to PPD (Richmond, Virginia, United States of America) where MPA levels will be measured via a proprietary validated method utilizing sensitive and selective high-performance liquid chromatography coupled with mass spectrometry. This method is applicable to the quantitation of MPA within a nominal range between 0.02 to 5.00 ng/mL and requires a 250- $\mu$ L aliquot of human serum. Timing of the initiation of sample analysis will be determined by the study monitor. The PPD staff performing the analysis will be blinded to the treatment assignment.

Source documentation for MPA will be maintained at PPD. The MPA results will be transferred electronically from PPD to FHI 360 for data management and analysis. The MPA results will not be documented on study CRFs or communicated to the study participants. No further testing of any remaining blood samples is planned; however, any remaining serum will be stored by PPD at least until the end of the study in the event of needed repeat testing or analysis of long-term stored sample stability. The PPD laboratory will discard remaining blood samples per PPD standard operating procedures (SOPs) upon receiving written approval from FHI 360. Any remaining aliquots stored on site will also be maintained until the end of the study, and only discarded after receiving written FHI 360 approval.

More detailed instructions on how to take, prepare, store, and send the serum samples for analysis in the central laboratory will be provided in the Study Manual.

# 6.2. Pharmacodynamics

Potential for contraceptive effect of TV-46046 when injected subcutaneously will be evaluated primarily based on its ability to suppress ovulation. While postovulatory maximum progesterone levels are usually greater than 16 nmol/L, progesterone levels used as a criterion of ovulation in contraceptive research usually range from 10 nmol/L to 16 nmol/L (approximately 3 to 5 ng/mL)

(Rahimy et al 1999, Brache et al 2012, Westhoff et al 2010, Jesam et al 2014). In addition, any rise in progesterone levels has to be sustained for at least 5 days to be consistent with ovulation. However, given the long-acting nature of TV-46046, anticipated irregular menstrual cycles, as well as the schedule of laboratory visits generally more than 5 days apart, it will not be possible to precisely define the timing within the luteal phase when elevated progesterone is detected. Therefore, measurement of sustained levels of progesterone for a presumption of ovulation will not be required in this study. The primary pharmacodynamics variable for this study will be ovulation defined as a single elevated serum progesterone  $\geq$ 4.7 ng/mL. The same approach was used previously in pharmacokinetic/pharmacodynamic studies of Depo subQ 104 (Jain et al 2004, Toh et al 2004).

During the pre-treatment phase ovulation will be confirmed in all women by measuring progesterone approximately twice a week during the approximately 2 to 3 weeks preceding their expected menses. Only women with confirmed ovulation will be enrolled in the study. During the pre-treatment phase of the study, if progesterone is at or above 4.7 ng/mL in at least 2 consecutive samples, ovulation will be considered confirmed for the purposes of the study eligibility.

All enrolled subjects will provide blood for progesterone measurement before the injection to document the baseline level of progesterone. During the study, all subjects will return for serum progesterone testing according to the pre-defined schedule (see Table 1). Serum progesterone results will be available within approximately 24 to 48 hours of specimen collection. Any time during the study, all women with initial serum progesterone  $\geq 3.0$  ng/mL will be asked to return within 5 days for repeated progesterone. If the repeated measurement within 5 days is at or below 3.0 ng/mL, the subject will continue follow-up per her visit schedule.

During the treatment phase of the study if progesterone is at or above 4.7 ng/mL in a single sample, ovulation will be considered confirmed for the purpose of the primary analysis. At any time during the study, any subject with initial progesterone  $\geq$ 4.7 ng/mL will be asked to return within 5 days for repeated progesterone measurement. Although repeated elevated progesterone is not needed for the primary definition of ovulation, this information will be used for more accurate ascertainment of ovarian function. Subjects with a single elevated progesterone measurement of  $\geq$ 4.7 ng/mL will be considered to have their ovulation restored.

Estradiol, an additional pharmacodynamic indicator, will be measured every time progesterone is measured. It will be used to more accurately characterize ovarian function.

At the discretion of the center investigator and/or based on accumulating data, additional sampling and testing for progesterone and estradiol may be conducted to ensure accurate ascertainment of the primary pharmacodynamic endpoint.
